5.3 Safety Assessments

On Day 1, the results of all assessments must be reviewed to assure that eligibility requirements are met before contacting the Central Randomization System for the subject's randomization assignment.

Subjects who discontinue will complete the Week 12/Early Termination (ET) Visit assessments for the corresponding period. Subjects who complete the study will complete the 30-day follow-up visit assessments. The Early Termination Visit should be as soon as possible after the last dose of study medication (investigational product) and prior to the subject receiving a prohibited concomitant medication.

All assessments should be performed or administered prior to study drug administration unless otherwise indicated.

Every effort must be made to ensure the same evaluator will complete the assessments for each subject at all visits.

Only data for the procedures and assessments specified in this protocol should be submitted to BMS on a case report form. Additional procedures and assessments may be performed as part of your institutional or medical practice standard of care; however, data for these assessments should remain in the subject's medical record and should not be provided to BMS, unless specifically requested from the sponsor. Safety assessments include the following:

- Adverse Events
- Safety laboratory values
- Physical examination
- Vital signs
- ECG

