All subjects who discontinue study drug should comply with protocol specified follow-up procedures as outlined in [Section 5](#). The only exception to this requirement is when a subject withdraws consent for all study procedures including post-treatment study follow-up or loses the ability to consent freely (ie, is imprisoned or involuntarily incarcerated for the treatment of either a psychiatric or physical illness).

If study drug is discontinued prior to the subject's completion of the study, the reason for the discontinuation must be documented in the subject's medical records and entered on the appropriate case report form (CRF) page.

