3.6 Post Study Drug Study Follow up

In this study, ACR20 and ACR70 and other efficacy measures are key endpoints of the study. Post study follow-up is of critical importance and is essential to preserving subject safety and the integrity of the study. Subjects who discontinue study drug must continue to be followed for collection of outcome and/or survival follow-up data as required and in line with Section 5 until death or the conclusion of the study.

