Subjects who discontinue at any time during the Treatment Period must complete the Early Termination (ET) Visit assessments							
Procedure	Day 1	Wk 2 (approx. D 15)	Wk 4 (approx. D 28)	Wk 8 (approx. D 56)	Wk 12 or ET (approx. D 84)	30 day FU Visit (approx. Day 114)	Notes
Safety Assessments							
Physical Exam	X				X	X	
Height and Weight	X				X	X	
ECG	X		X		X	X	Not required if early termination (ET) visit
Vital Signs	X	X	X	X	X	X	See Section 5.3.1 for details
Adverse Events Assessment	X	X	X	X	X	X	
Laboratory Assessments							
Hematology (CBC with differential)	X	X	X	X	X	X	
Chemistry panel	X	X	X	X	X	X	Must include liver function testing; see Section 5.3.5 for details. For double-blinded period, fasting glucose is required.
Estimated Glomerular Filtration Rate (eGFR) - AUDIT	X	X	X	X	X	X	As performed by Modification of Diet in Renal Disease (MDRD) Study equation
Fasting lipid panel	X			X	X	X	At least 10 hour fasting prior to collection of sample
IgM, IgA, and IgG	X		X		X	X	
Urinalysis	X				X	X	
Rheumatoid Factor	X				X	X	
Anti-CCP2	X		X		X	X	

Table 5.1-2: Flow Chart for Protocol IM006016 - Double-Blinded Treatment Period^a							
Subjects who discontinue at any time during the Treatment Period must complete the Early Termination (ET) Visit assessments							
Procedure	Day 1	Wk 2 (approx. D 15)	Wk 4 (approx. D 28)	Wk 8 (approx. D 56)	Wk 12 or ET (approx. D 84)	30 day FU Visit (approx. Day 114)	Notes
ANA	X				X	X	
Anti- Ro (SS-A) and Anti-La (SS-B)	X				X	X	
Urine pregnancy test	X		X	X	X	X	WOCBP only; results confirmed prior to administration of study drug. See Section 3.3.3
ESR (performed locally)	X	X	X	X	X	X	Performed locally. Every effort should be made to ensure the person analyzing the ESR results is not involved in the efficacy assessments (see Section 5.4)
hsCRP	X	X	X	X	X	X	
Pharmacokinetics	X	X	X	X	X		See Section 5.5.1 for details
Efficacy Assessments							
Tender (68)/ Swollen (66) Joint Count	X	X	X	X	X	X	Must have at least 6 swollen/tender joints prior to randomization
Subject Assessment of Pain	X	X	X	X	X	X	QoL assessments; see Section 5.8
Subject's Global Assessment of Disease Activity	X	X	X	X	X	X	
Physician's Global Assessment of Disease Activity	X	X	X	X	X	X	
Physical Function (HAQ-DI)	X	X	X	X	X	X	
Fatigue (VAS)	X				X	X	
SF-36	X				X	X	

Table 5.1-2: Flow Chart for Protocol IM006016 - Double-Blinded Treatment Period^a							

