7.6 Safety

Analysis of all safety data will follow the BMS standard safety data conventions^{[11](#) [12](#)} and supplements to the standard conventions as defined in this document.

The evaluation of drug safety is based primarily on clinical AE, laboratory abnormalities and vital signs reported during the study.

The summaries of AEs and laboratory marked abnormality during DB period will be provided by treatment groups. AEs and laboratory marked abnormalities will be included in the analysis of the DB period if the onset date is on or after first dose date and event occurs within 30 days post last dose date (DB period).

Frequency distribution and individual listings of all AEs will be generated. Laboratory marked abnormality using pre-defined abnormality criteria will also be descriptively summarized. There will be no statistical testing of group difference with respect to frequencies of AEs or laboratory marked abnormalities.

All recorded adverse events will be listed and tabulated by system organ class, preferred term, treatment and overall. Any physical examination findings will be listed. ECG, vital signs and clinical laboratory test results and corresponding change from baseline values will be listed and summarized by treatment. Values for ECG, vital signs and clinical laboratory test results outside the pre-specified criteria will also be listed and summarized. ECG readings will be evaluated by the Investigator and abnormalities, if present, will be listed.

Unless otherwise specified, baseline is defined as the last non-missing result with a collection date-time less than the date-time of the first dose of study medication, for laboratory results, vital signs and ECG.

Presentations for the DB period will be provided by “as treated” treatment group for as-treated analysis population, unless otherwise specified.

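### Protocol 5.3 as worded names the 30-day follow-up visit only for completers, in conflict with other protocol sections and with a SAP that counts and credits 30 days after last dose for early stoppers

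*Protocol*

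**What the plan says.** Protocol 5.3 assigns visits in two consecutive sentences. The first reads "Subjects who discontinue will complete the Week 12/Early Termination (ET) Visit assessments for the corresponding period"; the second reads "Subjects who complete the study will complete the 30-day follow-up visit assessments". The same paragraph asks for the ET visit promptly after the last dose.

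The heading of Table 5.1-2 says "Subjects who discontinue at any time during the Treatment Period must complete the Early Termination (ET) Visit assessments". It does not say that ET replaces follow-up, and the follow-up column is not limited to completers. That column is timed only as "30 day FU Visit (approx. Day 114". The ECG row carries the note "Not required if early termination (ET) visit".

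Other sections point towards follow-up for everyone:

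- Protocol 3.1 describes treatment for up to 12 weeks and then a 30-day follow-up period. SAP 2.1 repeats this.
- Protocol 3.5: "All subjects who discontinue study drug should comply with protocol specified follow-up procedures as outlined in" Section 5.
- Protocol 3.6: "Post study follow-up is of critical importance and is essential to preserving subject safety and the integrity of the study". It keeps subjects who stop drug under follow-up in line with Section 5.
- Protocol 3.6.1 keeps subjects who ask to stop drug in the study unless they refuse further contact.

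SAP 7.6 includes an AE or marked laboratory abnormality if its "onset date is on or after first dose date and event occurs within 30 days post last dose date (DB period". SAP 7.6.1 divides by all subjects with at least one dose. SAP 7.4.1 adds 30 days to the exposure of subjects who discontinue and describes those days as follow-up.

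**The concern.** A site that follows 5.3 as written would hold the ET visit and schedule nothing more. The analysis would still treat that subject as under observation for 30 days after the last dose. A completer would have laboratory tests, vital signs, an ECG and AE questioning at the end of dosing and again about 30 days later.

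Sites that read 3.1, 3.6 and the table differently would bring discontinuers back. Capture in the off-drug window would then depend on how each site resolves the conflict. Follow-up visits would be missing among subjects who stop early, some of whom stop because of an adverse event. New nonserious events and laboratory abnormalities in that window could be missed while the denominator and the exposure time stay intact.

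**Working it through.** This is mainly a reconciliation of text, with some day arithmetic. No sample size, power or error rate is involved.

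**1. Does any section give a discontinuer a visit after ET?** Sections 3.5 and 3.6 refer to Section 5 for the procedures, and 3.6.1 refers to those specified in the protocol. Within Section 5, the text of 5.3 names the 30-day visit only for completers, while Table 5.1-2 has a follow-up column with no restriction. So the sections that require follow-up rely on a section that is itself unclear.

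**2. When would the visit fall?** The table puts Week 12 at about Day 84, and 84 + 30 = Day 114, which reproduces the column heading. That day fits only a subject who doses to Week 12. For a last dose on Day 10 (an illustration), 30 days later is 10 + 30 = Day 40, and the SAP window closes there. A visit on Day 114 would be 114 − 10 = 104 days after last dose, so laboratory values taken then would lie outside the counted window. Timing therefore needs correcting even if the column applies to everyone.

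**3. How much of the window has no scheduled contact, under the literal reading of 5.3?** The documents give no interval between last dose and ET. Assume 0 to 7 days.

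- Days after the last scheduled contact = 30 − (days from last dose to ET).
- ET at 0 days: 30 − 0 = 30 (100%). ET at 7 days: 30 − 7 = 23 (77%).

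**4. What does the exposure rule credit?** SAP 7.4.1: (last dose − first dose + 1) + 30. For 28 days of dosing this gives 28 + 30 = 58 days. The part after the last scheduled contact is 23/58 = 40% to 30/58 = 52%.

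**5. Which post-dose ECGs are scheduled?** Table 5.1-2 has ECGs at Day 1, Week 4, Week 12 and follow-up. Assessments precede dosing unless otherwise indicated (5.3), so Day 1 is pre-dose.

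| Subject | No follow-up visit (literal 5.3) | Follow-up visit held |
|---|---|---|
| Stops before Week 4 visit | 0 | 1 (off drug) |
| Stops between Week 4 and Week 12 | 1 | 2 (one off drug) |
| Completes | not applicable | 3 (one off drug) |

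SAP 7.6.8.1 tabulates each subject's maximum post-dose QTcF, PR and QRS. A subject in the first row with no follow-up visit contributes nothing to those tables. The ET waiver does not forbid an ECG, but 5.3 also tells sites not to submit data from procedures outside the protocol unless the sponsor asks, so a voluntary one might not reach the database.

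**The case against.** A reader might infer from 5.3 that the protocol deliberately withholds follow-up from subjects who stop. The documents do not support that as a settled rule. The table leaves its follow-up column open, 3.1 gives a follow-up period after up to 12 weeks of drug, and 3.6.1 says that a subject who asks to stop drug stays in the study and so might still count as completing it. The SAP's 30-day credit suggests that its authors expected follow-up to happen. All of this stands. It makes the problem a contradiction to be reconciled.

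Nor does the lack of a scheduled visit mean that nothing is observed. Protocol 6.1.1 requires SAEs to be collected to 30 days after dosing stops and followed to resolution or stabilization. Section 6.2.1 requires follow-up of nonserious AEs that lead to discontinuation, and 6.3 does so for significant drug-related laboratory abnormalities. ET includes a physical examination, vital signs, AE review, hematology, chemistry and urinalysis. This is real mitigation for serious and already known events. It does not provide a contact at which new nonserious events or laboratory changes would be found.

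Protocol 3.3.1 puts five half-lives at about 3 days, so roughly 30 − 3 = 27 days of the window are essentially drug-free. The day counts above should not be read as lost exposure to drug. The SAP nevertheless chose to count the full 30 days.

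A reader might also infer that early stoppers have no ECG. The waiver covers only the ET visit and is an express exception to the table heading. Week 4 applies if reached, and the follow-up column includes an ECG.

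**Conclusion.** The conflict is real and should be resolved. As worded, 5.3 leaves subjects who discontinue without a scheduled contact after ET. That disagrees with Protocol 3.1 and 3.5 to 3.6.1, with Table 5.1-2, and with SAP 7.4.1 and 7.6. The Day 114 timing does not fit an early last dose under any reading.

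Under the literal reading, and assuming ET within 0 to 7 days of last dose, 23 to 30 of the 30 counted days follow the last scheduled contact. A subject who stops before Week 4 has no required post-dose ECG.

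Two further inferences go beyond the documents. One is that harm is under-counted on active drug in particular: no discontinuation data by arm are given, so this is only a possibility. The other is a count of affected subjects: no discontinuation rate is stated, and the planned 328 no longer holds because the synopsis says that recruitment stops before the planned number. The number affected cannot be derived.

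**What to change.** Reconcile Protocol 5.3 and Table 5.1-2 with Protocol 3.1, 3.5 to 3.6.1 and SAP 7.4.1 and 7.6:

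- In 5.3, state that the existing 30-day follow-up visit applies to all treated subjects, in addition to the Week 12 or ET visit. This includes subjects who discontinue and have not withdrawn consent to further contact.
- In Table 5.1-2, time that column from the last dose, with Day 114 kept as the expected day for subjects who dose to Week 12.
- In SAP 7.6.8.1, report by treatment the number of subjects with no post-dose ECG beside the ECG tables. With that in place the ET waiver can stay, since the follow-up visit already contains an ECG.

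The cost is protocol wording, one line in the ECG tables, and one visit already in the schedule for those who stop early.

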5.3.1 Adverse Event and Vital Sign Assessments

At Day 1 of the double-blind (DB) period, vital signs collection (blood pressure, heart rate, respiration rate, temperature) will occur prior to first dose of study medication is given from the assigned kit. At subsequent visits, vital sign collection will be completed prior to the administration of the dose of assigned study drug.

Subjects will be observed at the site for a minimum of 2 hours after receiving their first dose of study medication (tablets) on Day 1 of the DB Period The observation period should be extended if clinically indicated.

Any adverse events that occur will be reported on the appropriate eCRF (see [Section 6.1.1.](#))

All subjects who receive a dose of investigational product will be evaluated for safety testing. Safety outcomes include adverse events (AEs), clinically significant changes in vital signs, laboratory test abnormalities, and clinical tolerability of the investigational product. The Investigator will determine the severity of each adverse event as mild, moderate, severe, or very

severe. Laboratory findings which the investigator feels are clinically relevant should be recorded as adverse events. In addition, the investigator will determine the relationship of the AE to the administration of the investigational product.

Any incidental findings of potential clinical relevance that are not directly associated with the objectives of the protocol should be evaluated and handled by the Study Investigator as per standard medical/clinical judgment.

5.3.2 Tuberculosis Screening

Detailed medical and social history should be obtained to assess subject's risk for tuberculosis. Chest x-ray, physical examination, and medical history should be used to assess for active tuberculosis (TB).

Acceptable methods of testing for active or latent tuberculosis include tuberculin skin testing or Interferon release assays such as ELISpot or QuantiFERON® testing for tuberculosis. A tuberculin skin test will be performed and interpreted according to local country health authorities and/or medical society guidelines (ie, that provide recommendations for tuberculin skin testing for subjects who are to receive biologics, who are immunosuppressed, who have a prior history of BCG vaccination, or have a prior positive test).^{17,18,19,20,21} Tuberculin skin testing and interferon release assays are not contraindicated for persons who have been vaccinated with BCG.

After tuberculin skin testing is performed at screening, the 48 to 72 hour reading must be completed prior to administration of study drug. Negative test results for Interferon release assays should also be confirmed prior to administration of study drug.

If Interferon release assay results are indeterminate, one of two options for tuberculosis testing should be performed as follows: 1) The Interferon release assay test should be repeated. The second Interferon release assay result will replace the first test result. 2) Tuberculin skin testing should be performed as an alternative method of screening. If the second Interferon release assay test result is also indeterminate, tuberculin skin testing should be performed and the subject should not be enrolled into the study until a negative tuberculin skin test is documented.

5.3.3 Electrocardiogram

A 12-lead electrocardiogram (ECG) will be recorded at the times noted in the Time and Events [Table 5.1-1](#) and [Table 5.1-2](#))

5.3.4 Physical Examination

A complete medical history will be obtained at the screening visit.

Complete and/or interim physical examinations may be performed by a Doctor of Medicine (MD), Doctor of Osteopathy (DO), Physician's Assistant (PA), or Nurse Practitioner (NP). While the interim physical examination may not be as comprehensive as the initial full examination, key aspects of the interim examination should evaluate important body systems as

clinically indicated. These body systems include at a minimum, the heart, lungs, abdomen, and skin. Evaluation of lymph nodes, liver, spleen, breast and other body systems is at the discretion of the examiner. An interim physical examination may note any changes in the subject's condition (body systems) since the last assessment and does not preclude examination of any of the body systems as clinically indicated.

Every effort should be made to ensure the same evaluator will complete the physical examination for each subject at specified visits throughout the study. Documentation of who performed the examination is to be recorded in source notes.

5.3.5 Laboratory Test Assessments

A central/local laboratory will perform the analyses and will provide reference ranges for these tests.

Detailed instructions on the collection, processing, and shipping of all blood and urine samples will be provided to the investigator in a separate manual at or before the time of study initiation.

The following clinical laboratory tests will be performed:

Hematology

Hemoglobin
Hematocrit
Total leukocyte count, including differential
Platelet count

Serum Chemistry

Aspartate aminotransferase (AST)	Total Protein
Alanine aminotransferase (ALT)	Albumin
Total bilirubin	Sodium
Direct bilirubin	Potassium
Alkaline phosphatase	Chloride
Lactate dehydrogenase (LDH)	Calcium
Creatinine	Phosphorus
Blood Urea Nitrogen (BUN)	Magnesium
Uric acid	Creatine kinase
Fasting glucose (for screening, PI discretion if fasting is needed. For double-blinded period, fasting is required)	Liver function testing

Lipid Panel (includes fasting lipids)

ESR (local lab)

hsCRP

Urinalysis

Protein
Glucose

Blood

Leukocyte esterase

Specific gravity

pH

Microscopic examination of the sediment if blood, protein or leukocytes esterase are positive on the dipstick

Serology

Serum for hepatitis C antibody, hepatitis B surface antigen, hepatitis B core antibody, hepatitis B surface antibody

Auto-immune serology: ANA, Anti-Ro, Anti-La, Anti CCP2, Rheumatoid Factor

Immunoglobulin levels: IgM, IgA and IgG.

HIV testing (investigator discretion; local lab)

Other Analyses

Pregnancy test (WOCBP only: screening, predose, discharge).

Follicle stimulating hormone (FSH) (screening only for women only)

Results of all laboratory tests required by this protocol must be provided to BMS, either recorded on the laboratory pages of the CRF or by another mechanism as agreed upon between the investigator and BMS (eg, provided electronically). If the units of a test result differ from those printed on the CRF, the recorded laboratory values must specify the correct units. Any abnormal laboratory test result considered clinically significant by the investigator must be recorded on the appropriate AE page of the CRF (see [Section 6.1.1](#)).

5.4 Efficacy Assessments

Efficacy assessments are described in the following sections. See [Appendix 3](#) for detailed definitions.

5.4.1 Primary Efficacy Assessment

- ACR20 response rate at Week 12
- ACR70 response rate at Week 12

5.4.2 Secondary Efficacy Assessments

- Signs and Symptoms: ACR20/ACR50/70 over time
- Remission and change from baseline: DAS28-CRP, DAS-ESR, SDAI, CDAI, Boolean over time
- PK: predose concentration (C_{trough}) of BMS-986142 at time-points specified in [Table 5.5.1-1](#)
- MRI assessment of change from baseline in synovitis, osteitis (bone marrow edema), bone erosion and cartilage loss (joint space narrowing) in hands/wrists at timepoints specified in [Table 5.1-2](#)

[REDACTED]

5.4.4 **Imaging Assessments**

Any incidental findings of potential clinical relevance on chest x-ray or any additional imaging performed that are not directly associated with the objectives of the protocol should be evaluated and handled by the Study Investigator as per standard medical/clinical judgment. Images will be submitted to imaging core lab for central analysis. Assessment of hand and wrist MRI by Investigator is not expected.

5.4.4.1 **MRI Assessment**

MRI scanners used in the study must be deemed qualified by BMS/assigned Imaging Core Lab prior to subject scans. The hand/wrist that is clinically most swollen at Screening Visit will be imaged using a whole body MRI system. Of note, the Screening Visit MRI is considered the baseline MRI assessment for this study. The SAME hand/wrist that was imaged at Screening will be imaged at Week 4, and Week 12 on the SAME MRI scanner as was used at screening. The Screening Visit MRI is to be performed approximately 14 days prior to randomization. Week 4 and Week 12 MRIs are to be performed \pm 7 days of the scheduled Week 4 visit and Week 12 visit, respectively. **Subjects who terminate the study early require an MRI at the early termination (ET) visit only if ET < 4 weeks or > 8 weeks from date of randomization and should have their early termination (ET) MRI NO MORE than 7 days from their Early Termination (ET) Visit.**

Sites should schedule two MRI appointments with radiology department 7 days apart in the event that a MRI exam needs to be repeated due to technical difficulties. Technical issues with MRI identified at the investigator site or Imaging Core Lab should be re-imaged within 7 days of notification.

Subjects with severe renal insufficiency (ie, estimated glomerular filtration rate (eGFR) or GFR < 30 mL/min/1.73m²), will be excluded from the study, as they are at increased risk of

Nephrogenic Systemic Fibrosis, a rare, but serious, condition associated with the use of gadolinium-based MRI contrast agents.

Synovitis, osteitis (bone marrow edema), bone erosion and cartilage loss (joint-space narrowing) will be scored according to the OMERACT RAMRIS²². Change at follow-up from baseline in each RAMRIS score will be calculated. Scoring will be performed centrally by 2 independent, experienced readers who will be blinded to clinical details, radiographic findings, treatment arm and MRI sequence (Screening, Week 4, Week 12, and/or ET, if applicable).

Additional information is provided in a separate MRI imaging manual.

